11.3.2 Analysis Plan

Differences in length of stay between arms will be tested using a two-sample, two-sided t-test. Wilcoxon nonparametric testing will be used for analyzing continuous outcomes that are skewed and not approximately normally distributed. Fisher's exact tests will be used to test for differences in categorical variables between arms. All tests will be two-sided with a 0.05 significance level. Linear models will be created to test the effects of treatment after adjusting for the baseline characteristics of age, gender, and lung function.

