2.2 Secondary objectives

2.2.1 To prospectively determine the effect of 10 sessions of customized preoperative PR on the number of postoperative complications in patients that undergo a lung cancer resection and have COPD compared to a matched control group.

Hypothesis: Ten sessions of customized preoperative PR will significantly reduce the number of postoperative pulmonary complications.

2.2.2 To prospectively determine the effect of a 10-session preoperative PR on the trajectory of quality of life at 3 and 6 months after the curative resection compared to a matched control group.

Hypothesis: Ten sessions of customized preoperative PR will significantly and meaningfully (more than the minimal clinically important difference) improve quality of life after surgery compared to a control group.

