11.4 Supplementary Analysis Plans

11.4.1 Secondary Endpoints

End points that will address AIM 2 (baseline and at 3 and 6 months after hospital discharge):

Post-Operative Pulmonary Complications: The following events will be considered post-operative pulmonary complications: pneumonia (new infiltrate + either fever (>38.5 C) and white cell count $>11,000$ or fever and purulent secretions), severe atelectasis (requiring bronchoscopy), prolonged chest tubes (>6 days), and respiratory failure (intubation or prolonged mechanical ventilation (>24 hours)). These outcomes will be obtained by chart review by a nurse trained in the abstraction of the desired outcomes from the medical records and blinded to treatment assignment.

Chronic Respiratory Questionnaire (CRQ) (four domains: dyspnea, fatigue, emotional function and mastery). This instrument will be the primary tool to assess QoL given that it was specifically designed for COPD. Specifically, the CRQ represents one of the most well-known, widely-applied, and psychometrically-sound patient reported outcomes for use in clinical trials involving patients with COPD. The CRQ has been validated and has demonstrated a reliable quality of life measures for patients with chronic airflow limitations. A 0.5 point will be considered significant and was considered in the sample size calculation as that difference as is the well-established MCID (minimally clinically important difference) for the instrument. Analysis for the QOL outcomes will be identical to that for the primary endpoint. We include the scores from the dyspnea questionnaire under the generic umbrella term as a domain of QOL.

LASA (single-item numerical analogue quality of life Questionnaire) individual QOL domain scores. All of these questionnaires have been validated previously for lung cancer patient populations and for assessment of patient-reported outcomes in similar trials. LASA items have been validated as general measures of global QOL dimensional constructs in numerous settings and have been constructed and validated at Mayo Clinic for use in cancer patients. These single-item assessments have become the most used assessments in all NCI-sponsored cancer control studies.²⁸

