11.4.2 Secondary Analysis

Longitudinal analysis for the relationship between QOL and the intervention will be handled by repeated measures analysis of variance modeling and multiple regressions. Finally, a logistic regression model will be used to identify which variables are most closely associated with the dependent variable of patients who experience either clinically significant deficits in QOL (one regression model). The modeling processes will include the aforementioned covariates to control for spurious correlations.

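### The secondary quality-of-life aim has no deciding CRQ domain, visit or method, and all of its tests run at an unadjusted two-sided 0.05

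*Combined protocol and SAP*

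**What the plan says.** - **Aim.** Objective 2.2.2 concerns the "trajectory of quality of life at 3 and 6 months after the curative resection". Its hypothesis is that PR "significantly and meaningfully (more than the minimal clinically important difference) improve quality of life after surgery compared to a control group". No score, visit or test is named.
- **Scores.** Section 11.4.1 lists the CRQ with "four domains: dyspnea, fatigue, emotional function and mastery" and says "This instrument will be the primary tool to assess QoL given that it was specifically designed for COPD". No total score or lead domain is given. The same section adds the individual LASA scores and counts a dyspnea questionnaire as a QOL domain.
- **Meaningful difference.** Section 11.4.1 sets it at 0.5 point for the CRQ. None is given for LASA or MRC.
- **Methods.** Section 11.4.1 says "Analysis for the QOL outcomes will be identical to that for the primary endpoint". Under Section 11.3.2 that means a t-test or Wilcoxon test plus adjusted linear models. Section 11.4.2 says "Longitudinal analysis for the relationship between QOL and the intervention will be handled by repeated measures analysis of variance modeling and multiple regressions". Neither is called decisive.
- **Error rate.** Section 11.3.2: "All tests will be two-sided with a 0.05 significance level". No multiplicity rule appears.
- **Power.** Section 11.2.1 claims at least 80% power for each aim with 97 patients per arm, including 10% for attrition, and half a standard deviation for QOL.

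**The concern.** The QOL aim has a formal hypothesis and a power claim of its own, so readers will expect a yes-or-no answer. The plan does not say which result gives it. With four CRQ domains, two visits and two families of methods, each at 0.05, the analyst can choose after seeing the data which result answers the aim. A claim that PR improves QOL could then rest on one chance finding, with an aim-level error rate that nobody has set. Length of stay, the primary endpoint, is not affected.

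**Working it through.** **1. The plan's own power figure.** From Section 11.2.1, 97 × 0.9 = 87.3, so 87 evaluable per arm. For 0.5 SD, the noncentrality is 0.5 × √(87/2) = 3.30. The two-sided 0.05 t-test then has 91% power, so the claim of at least 80% holds for one QOL test. The plan states no aim-level error rate for QOL, so there is none to reproduce.

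**2. Number of tests (score by visit).**
- CRQ only: 4 × 2 = 8.
- CRQ, MRC and LASA with 5 items (Section 9.3): (4 + 1 + 5) × 2 = 20.
- The same with the 6 LASA items printed in Appendices I and II: (4 + 1 + 6) × 2 = 22.

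The last two counts assume that the dyspnea questionnaire in Section 11.4.1 is the MRC scale, which the study calendar schedules at both visits.

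**3. Chance of at least one false positive.** If independent, this is 1 − 0.95^k in either direction and 1 − 0.975^k in PR's favour. For k = 8 that gives 1 − 0.95^8 = 0.337 and 1 − 0.975^8 = 0.183. The correlated figures come from simulating multivariate normal test statistics. The documents give no correlations, so those below are assumptions (between scores / between visits).

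| Tests | Direction | Independent | 0.3 / 0.5 | 0.5 / 0.6 | 0.7 / 0.7 |
|---|---|---|---|---|---|
| 8 (CRQ) | either | 34% | 30% | 26% | 21% |
| 8 (CRQ) | favours PR | 18% | 15% | 13% | 10.5% |
| 20 | either | 64% | 55% | 45% | 33% |
| 20 | favours PR | 40% | 29% | 23% | 16.5% |
| 22 | either | 68% | 58% | 48% | 34% |
| 22 | favours PR | 43% | 31% | 24% | 17% |

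A single two-sided 0.05 test gives 5% and 2.5%.

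**4. Choice of method.** This is not in the counts above. Two methods on one score whose test statistics correlate 0.8 to 0.95 (assumed) give 7.7% to 6.5% instead of 5%, a small addition.

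**5. Adding the MCID condition on the CRQ.** At 87 per arm the smallest significant difference is 1.96 × √(2/87) = 0.297 SD. The 0.5-point MCID is therefore the stricter condition when the SD is below 0.5/0.297, about 1.7 points. The documents give no CRQ SD. For three assumed values, the standard error (SE) is SD × √(2/87), and z is 0.5/SE:

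| SD | SE | z needed | One test | 8 tests, independent | 8 tests, correlated as above |
|---|---|---|---|---|---|
| 1.0 | 0.152 | 3.30 | 0.05% | 0.4% | 0.3–0.4% |
| 1.2 | 0.182 | 2.75 | 0.30% | 2.4% | 1.6–2.2% |
| 1.5 | 0.227 | 2.20 | 1.4% | 10.6% | 6–9% |

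**6. Power under a four-domain Holm procedure.** The strictest step is 0.05/4 = 0.0125. Averaging two visits with correlation r, and the same 0.5 SD effect at each, gives a standardised effect of 0.5/√((1 + r)/2). For r = 0.5 this is 0.577, with 90% power at 0.0125. For r = 0.6 it is 0.559 and 88%. For r = 0.8 it is 0.527 and 83%. A single-visit test at 0.0125 would have 78%. The values of r are assumptions.

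**The case against.** Four points on the other side have force.

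- **The CRQ is named as the main tool.** This stands, and it makes 8 the family closest to the plan. A reader might infer that any of 20 to 22 tests can carry the aim and that a chance benefit is therefore likely. The documents do not support that. They put the CRQ first, and even for 22 independent tests the chance of a result favouring PR is 43%, below one half. Only the either-direction figures pass one half, and they include results favouring control.
- **The hypothesis requires more than significance.** It asks for a difference above the MCID, so it would be wrong to say that the plan accepts one favourable p-value as success. No section says so. If the condition were enforced, the CRQ false-benefit chance would be small at an SD of 1.0 or 1.2. However, no test in Sections 11.3.2 to 11.4.2 includes it, its protection depends on an SD that the plan does not give, and LASA and MRC have no MCID.
- **The aim concerns a trajectory, and a longitudinal model is planned.** Separate by-visit tests are thus not the only reading. But Section 11.4.1 applies the primary-endpoint method to QOL, and Section 11.4.2 names no deciding contrast.
- **The 0.05 is a per-test level and the aim is secondary.** Both are true. The plan breaks no aim-level promise, because it makes none. The fault is that a formally hypothesised and powered aim has no decision rule.

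**Conclusion.** The point holds as a gap in the decision rule for a secondary aim. The plan names no deciding CRQ domain, visit or method and sets no multiplicity control. On the CRQ alone, the chance of at least one p<0.05 under no effect is 34% if independent and about 21–30% if correlated. In PR's favour it is 18%, or about 10–15%, which is roughly 4 to 7 times the 2.5% of one test. Counting MRC and LASA raises it. Enforcing the 0.5-point MCID would bring the CRQ benefit figure to about 0.3–0.4% at an SD of 1.0, 2% at 1.2 and 6–11% at 1.5. The correlations and SDs are assumptions. The absence of a rule is plain from the text and does not depend on them. It should be corrected, but it does not touch the primary analysis.

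**What to change.** In Sections 11.4.1 and 11.4.2, state that:

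- aim 2.2.2 is decided by the CRQ only;
- each domain has one treatment contrast, averaged over 3 and 6 months, from the planned repeated-measures model;
- the four contrasts are Holm-adjusted at two-sided 0.05;
- the 0.5-point MCID is applied to the estimate, as the hypothesis says;
- by-visit, LASA and MRC results are supportive and are reported with confidence intervals.

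**Cost.** No extra patients or data are needed. At 87 per arm and 0.5 SD, power for significance in one domain at the strictest Holm step is about 83–90% (assumed visit correlation 0.8 to 0.5). That compares with 91% for a single unadjusted visit test and remains above the stated 80%. By-visit differences become supportive only, so the team must accept the average over the two visits as its answer on the trajectory.

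These power figures cover significance alone. Half an SD and 0.5 point are the same effect only if the SD is 1.0. In that case the true effect equals the MCID, and the estimate exceeds it only about half the time. That follows from the hypothesis as already written, not from the Holm adjustment, but the plan should state the CRQ SD it assumes.

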4.4 Patient Registration Requirements

Registration is to take place after surgery is scheduled.

Informed consent:

The patient must be aware of the neoplastic nature of his/her disease and willingly consent after being informed of the intervention, the experimental nature of the intervention, alternatives, potential benefits, and discomforts. Current human protection committee approval of this protocol and a consent form is required prior to patient consent and registration. Patients may be enrolled in other clinical trials while participating in this study.

Patient Completed Booklets and Other Patient Materials:

Patient questionnaire booklets to be administered at baseline are to be ordered prior to the registration of any patients. Patient completed booklets can be ordered by downloading and completing the booklet order form (located under the supplemental documents section of the A221502 web site) and faxing the form to Attn: Operational Support Clerk at [REDACTED]. Samples of the booklets are found in Appendices I and II, which are to be used for reference and IRB submission only. They are not to be used for patient completion.

The patient materials listed in section 5.4 must also be ordered prior to registration of any patients. Instructions for ordering these materials are provided in section 5.4.

Patient Release of Medical Records:

Medical records from admission to discharge must be submitted per Section 5.5. Patients must complete the institution's own Authorization for Release of Medical Records prior to registration.

Limited access information:

This is a limited access study. Each participating Alliance member site must be individually approved by the study chair or designate and be listed as a participating site on the cover page of the protocol. All participating sites will be approved by the study chair prior to being listed on the protocol cover page.

To become a participating site, please email [REDACTED] at [REDACTED]. Please include the names of the institution, CTEP Institution ID, Surgeon(s), PR Specialist(s) and Institutional Coordinator. See Section 5.2.

4.5 Patient Registration/Randomization Procedures.

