4.6 Stratification Factors

Randomization will be stratified (equal number in both groups) by 3 variables that may bias the results if they become unbalanced after randomization:

4.6.1 Very severe lung function defined as one of the following: (FEV1 <30% predicted) or use of permanent oxygen or PCO₂ >50mmgh])

Yes vs. No

NOTE: If the patient has no lung function test it will be considered NOT very severe lung function.

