4.6.2 Prior Neo-adjuvant chemotherapy for this operation

Yes vs. No

4.6.3 Open thoracotomy vs. video assisted thoracoscopy (VATS).

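### Randomisation is stratified on three factors, but the length-of-stay test uses none of them and two enter no analysis, so the plan is valid but conservative if they predict stay

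*Combined protocol and SAP*

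**What the plan says.** Section 4.6 states: "Randomization will be stratified (equal number in both groups) by 3 variables that may bias the results if they become unbalanced after randomization". The three variables are:

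- very severe lung function, a yes/no composite of FEV1, permanent oxygen and PCO2;
- "Prior Neo-adjuvant chemotherapy for this operation", yes or no;
- open thoracotomy versus VATS.

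For the first, a note adds: "If the patient has no lung function test it will be considered NOT very severe lung function". The factor therefore has a value for every patient. Section 4.4 says "Registration is to take place after surgery is scheduled", so the planned approach is known at registration.

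Section 11.3.2 gives the primary test: "Differences in length of stay between arms will be tested using a two-sample, two-sided t-test". It continues: "Wilcoxon nonparametric testing will be used for analyzing continuous outcomes that are skewed and not approximately normally distributed". It then adds: "Linear models will be created to test the effects of treatment after adjusting for the baseline characteristics of age, gender, and lung function". It does not say which lung-function variable is meant. Section 11.4.2 reuses those covariates, and section 11.4.1 analyses quality of life in the same way as the primary endpoint. No section uses surgical approach or neoadjuvant chemotherapy in an analysis.

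Section 11.2.1 sizes the trial at 97 per arm with a 10% attrition allowance, for at least 80% power to detect 3 days.

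**The concern.** Stratified allocation balances the arms on the three factors, so the difference in mean stay varies less from trial to trial than under simple randomisation. An unstratified t-test does not credit this. Its standard error still contains the variation between strata. If the factors predict stay, the reported standard error is too large, the test rejects less often than 5% under the null, and some power is lost. The adjusted models in section 11.3.2 do not repair this, because they omit surgical approach and neoadjuvant chemotherapy.

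The undefined lung-function covariate adds a smaller problem. The stratification factor exists for everyone, whereas a measured FEV1 would be missing for untested patients.

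At stake are the width of the primary interval and a few points of power. The validity of the result is not at stake.

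**Working it through.** **1. The plan's own figure.** 97 × 0.90 = 87.3, so 87 per arm and 174 evaluable. The 80% power for 3 days cannot be reproduced, because no SD is given. Solving backwards, the standard error must be 3 / (1.960 + 0.842) = 1.071, so SD = 1.071 / √(2/87) = 7.06 days (7.02 with the t distribution). This is an upper bound, because section 11.2.1 promises at least 80%.

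**2. Closed form.** Let R² be the share of the variance of stay explained by the factors (assumed), with perfect balance. The t-test reports SE = 1.071, but the true value is SE × √(1 − R²).

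- Null rejection, unadjusted: 2Φ(−1.96 / √(1 − R²))
- Power, unadjusted: Φ((3 − 1.96 SE) / (SE √(1 − R²)))
- Power, adjusted: Φ(3 / (SE √(1 − R²)) − 1.96)

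At R² = 0.10, √0.90 = 0.949 and the true SE is 1.016. Null rejection is 2Φ(−2.066) = 3.9%. Unadjusted power is Φ(0.901 / 1.016) = Φ(0.887) = 81.2%. Adjusted power is Φ(2.953 − 1.96) = 84.0%.

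| R² | Null, unadjusted | Power, unadjusted | Power, adjusted | Gain (points) |
|---|---|---|---|---|
| 0 | 5.0% | 80.0% | 80.0% | 0 |
| 0.05 | 4.4% | 80.6% | 82.0% | 1.4 |
| 0.10 | 3.9% | 81.2% | 84.0% | 2.8 |
| 0.20 | 2.8% | 82.7% | 87.9% | 5.2 |
| 0.30 | 1.9% | 84.3% | 91.8% | 7.5 |

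**3. Simulation with skewed stay.** All inputs are assumptions: 174 patients, permuted blocks of 4 in eight strata, lognormal stay in whole days, total SD 7, control mean 8/10/12 days, 10,000 trials per cell. Strong strata are 10% very severe (×1.3), 15% neoadjuvant (×1.2) and 40% open (×1.6). Weak strata use ×1.15, ×1.1 and ×1.3. The section 11.3.2 model takes lung function as the stratification factor.

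| Strong strata, mean 8/10/12 | Null rejection | Power for 3 days |
|---|---|---|
| t-test | 3.6/3.7/2.7% | 85.2/83.9/84.0% |
| Section 11.3.2 linear model | 3.8/3.8/3.1% | 84.9/83.7/83.9% |
| Linear model, three factors | 4.5/5.0/4.9% | 86.6/86.8/88.3% |

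- The gain over the t-test is 1.4/2.9/4.3 points. A separate simulation of the same design gave null rejection of 4.6/3.5/2.6% for the t-test against 5.5/5.1/4.0% with the three factors, and gains of 1.8/2.3/4.2 points.
- The t-test reports a standard error of 7 × √(2/87) = 1.06. The actual SD of the estimate is 1.01/0.99/0.96. The ratios are 1.05/1.07/1.10, so the interval is about 5–10% too wide.
- Weak strata: null rejection is 4.5/4.4/4.0% against 4.8/5.0/4.6%, and the gain is 0.4/0.8/1.3 points.
- No stratum effect: power changes by −0.1/−0.2/+0.1 points.
- SD 5, strong strata: null rejection is 3.4/2.0/1.6% against 5.3/4.5/5.0%. Power is about 99% either way, so the gain there is mainly a correct interval.

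**4. Rank test against linear model.** In the SD 7 setting the Wilcoxon test has 85.7–94.8% power for 3 days, against 81.1–87.8% for the three-factor linear model. Compared within scenario, the rank test leads by about 4–9 points with weak or no strata. With strong strata the unstratified rank test leads by about 1–8 points, and a rank test adjusted for the factors by about 4–8.

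**5. Definition of lung function.** If FEV1 were the covariate and untested patients were dropped, 80% power at SD 7.02 would fall to 78/76/71% with 5/10/20% untested (assumed shares).

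**The case against.** The strongest reply is that nothing is invalid. Section 4.6 worries about bias from imbalance, and stratified allocation is itself the remedy. An unadjusted test afterwards keeps its level and at least its planned power. The gain depends on stratum effects that the documents do not give, and it is close to nil when those are small. All of this stands, and it limits the point to precision.

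The second reply concerns the remedy. If stay is skewed, section 11.3.2 may lead to a Wilcoxon test, and under lognormal stay that test has more power than a linear model in days. This also stands. Replacing a rank test by a linear model would be a trade-off, so the fix must not require that Wilcoxon be barred. It does not answer the main point, because the unstratified Wilcoxon test ignores the strata too.

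A reader might infer several stronger things that the documents do not support:

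- **Bias or inflated false positives from omitting the factors.** The direction is the opposite: the test is conservative.
- **Inflation from the undefined choice between t-test and Wilcoxon.** Picking whichever test is significant would give 6.4–6.7% under a null with skewed stay. The plan's trigger, however, is the shape of the distribution, not the result. A normality rule (assumed) applied as stated gives 4.5–5.1% with weak or no strata, and 3.4/3.8/2.6% with strong strata. The missing criterion is a missing detail.
- **A flaw in how deaths before discharge are counted.** The plan is silent on this. A line on it would be a useful but optional clarification, outside this point.

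**Conclusion.** The point holds as a matter of precision. The named length-of-stay test uses none of the three stratification factors. The linear models use at most one, and only if lung function means the section 4.6 factor. Surgical approach and neoadjuvant chemotherapy are used nowhere.

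At an assumed SD of 7 with 174 patients, the t-test rejects a true null in about 2.6–4.6% of trials with strong strata. Adding the factors brings this to about 5%, corrects an interval some 5–10% too wide, and gains about 2–4 points of power (1.4 in the lowest cell). With weak strata the gain is about 1 point. If the factors do not predict stay, there is none. These sizes rest on assumed SD, mean stay, prevalences and effects. The textual gap rests on no assumption.

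The change should be made because it is nearly free. The trial would be interpretable without it.

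**What to change.** In section 11.3.2, before comparative data are seen:

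- Include the three randomisation factors, as recorded at randomisation, in the primary length-of-stay comparison and in the linear models. Use the planned approach, neoadjuvant yes/no, and the section 4.6.1 yes/no definition of lung function. Age and gender may stay.
- If the t-test is to be primary, replace it with a linear model in days with treatment and the three factors. Report the adjusted mean difference with its 95% interval.
- If the Wilcoxon test is to be primary, use its stratified (van Elteren) form and report the adjusted mean difference in days alongside.
- Name which of the two decides the hypothesis, and label the other a sensitivity analysis.
- In section 11.4, say whether the quality-of-life analyses use the same factors, since they borrow the primary method.

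State the trade-off when choosing. The rank test is likely to have more power if stay is strongly skewed, but it does not estimate the 3-day mean difference on which section 11.2.1 sized the trial.

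The cost is wording only. The factors are already recorded for randomisation and the sample size is unchanged. Adjustment uses three degrees of freedom, with a power change between −0.2 and +0.1 points if the factors do not predict stay. Keeping age and gender as well costs 0.3–0.5 points if none of the five predicts stay.

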3.2 Eligibility Criteria

Use the spaces provided to confirm a patient's eligibility by indicating Yes or No as appropriate. It is not required to complete or submit this page.

- **3.2.1** Patient is scheduled to undergo NSCLC resection: video assisted thoracoscopy (VATS) or open thoracotomy for: limited resection, lobectomy, or pneumonectomy. Surgery must not be scheduled to take place < 3 weeks after registration.
- **3.2.2** Patient has a doctor diagnosis of COPD.
- **3.2.3** Patient is a current or ex-smoker with a smoking history of ≥ 10 pack years. (Calculated by multiplying the number of **packs** of cigarettes smoked per day by the number of years the person has smoked. For example, 1 **pack-year** is equal to smoking 20 cigarettes (1 **pack**) per day for 1 **year**, or 40 cigarettes per day for half a **year**, and so on).
- **3.2.4** Age ≥ 18 yrs.

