11.3 Statistical Design and Analysis for the Primary Endpoint

11.3.1 Primary Endpoint

End point that will address AIM 1: hospital length of stay. The coordinator at each site will be responsible for sending complete de-identified hospital records from each patient to [name] staff, where a nurse blinded to the study arm will abstract the main outcome (length of stay and postoperative complications). See Section 6.3.

The primary endpoint will be assessed at [name] office (Mayo Clinic) with the complete admission hospital records in order to extract the length of stay. The records will be mailed from the sites to [REDACTED] in a pre-stamped envelope. See Section 6.3.

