APPENDIX III: PAIN SCALE & HOSPITAL EXPERIENCE

Patient Initials: _____ Date: _____

Patient Number: _____

Directions: Please circle the answer that best reflects the level of pain that you experienced after you were discharged from the hospital.

1. Please rate your pain by using the number that best describes your pain at its worst in the last two weeks?

2. Please rate your pain by using the number that best describes your pain at its least in the last two weeks?

3. How would you rate your hospital experience?

APPENDIX IV: CHECKLIST FOR MEDICAL RECORDS**PULMONARY REHABILITATION BEFORE LUNG CANCER RESECTION**

Admission Date: _____ Discharge Date: _____ ID Number: _____

Please provide the following documents related to the Lung Surgical Resection for this study.

	YES	NO
Admission Report (Admitting history and Physical Exam)		
Operative Report (Description of procedure performed and Number of chest tubes placed)		
Discharge Summary (Dismissal information including location Subject dismissed to i.e. home, rehab facility, etc.)		
Progress Report (Daily notes including description of any complications)		
Reports of results from: Radiology (Report only, images not needed)		
Blood/Lab Draws		

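### The adjusted length-of-stay model omits planned extent of resection and two stratification factors; this costs precision in that model and does not affect the unadjusted primary test

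*Combined protocol and SAP*

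**What the plan says.** The primary endpoint is set in 11.3.1: "End point that will address AIM 1: hospital length of stay". Section 11.3.2 gives the test, "Differences in length of stay between arms will be tested using a two-sample, two-sided t-test", with the alternative "Wilcoxon nonparametric testing will be used for analyzing continuous outcomes that are skewed and not approximately normally distributed". Neither uses covariates. A later sentence in the same section adds: "Linear models will be created to test the effects of treatment after adjusting for the baseline characteristics of age, gender, and lung function". The plan does not call this model primary.

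Eligibility (3.2.1) covers "video assisted thoracoscopy (VATS) or open thoracotomy for: limited resection, lobectomy, or pneumonectomy". On timing, 4.4 says: "Registration is to take place after surgery is scheduled". The three stratification factors in 4.6 are very severe lung function, neo-adjuvant chemotherapy, and open thoracotomy versus VATS. They were chosen because imbalance in them might bias the results. Extent of resection is not among them, and 11.7 lists no descriptive factors.

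The record of the operation named in the Appendix IV checklist is "Operative Report (Description of procedure performed and Number of chest tubes placed", which is the operation carried out and not the one planned.

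The covariate list reaches beyond length of stay. Section 11.4.1 analyses QOL in the same way as the primary endpoint, and 11.4.2 carries the covariates mentioned earlier into the secondary models.

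**The concern.** An adjusted model is useful when it contains baseline variables that predict the outcome. Operations ranging from limited resection to pneumonectomy could well differ in expected stay. That is clinical reasoning; the documents give no figure for it. The planned operation should be known at registration, because surgery is scheduled by then. The protocol already relies on one planned feature of the operation at that moment, since open versus VATS can only be the planned approach when the patient is randomised.

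Approach and neo-adjuvant chemotherapy are missing from the model too, although the protocol singles both out as variables whose imbalance matters. The third stratification factor is at most partly covered by lung function, which 11.3.2 does not define.

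At stake are the standard error of the adjusted treatment effect and its robustness to a chance difference in case mix, for length of stay and for the QOL models that inherit the list. There is also a practical risk. If planned extent is not recorded prospectively, the operative report cannot replace it, because the procedure performed is known only after randomisation.

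**Working it through.** **Inputs.** 97 per arm, 10% attrition, 80% power and a 3-day difference in stay (11.2.1); two-sided 0.05 (11.3.2). Evaluable per arm: 97 × 0.9 = 87.3, taken as 87. No SD for length of stay is stated.

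**The plan's own figure.** Without an SD, the 80% cannot be reproduced independently. It can only be solved backwards:

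SD = 3 / [(1.960 + 0.842) × √(2/87)] = 3 / (2.802 × 0.1516) ≈ 7.06 days (7.02 with the t distribution).

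The stated size is therefore consistent with 80% power if the SD is about 7.06 days. At 87 per arm, an SD of 6, 7 or 8 days would give 91.0%, 80.7% or 69.6%.

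**Effect of adding planned extent.** Let R² be the share of length-of-stay variance explained by planned extent (an assumption). Then:

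- residual SD = 7.06 × √(1 − R²)
- SE of the difference = residual SD × √(2/87)
- power = Φ(3/SE − 1.960)
- equivalent unadjusted size per arm = 87/(1 − R²)

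| R² | Residual SD | SE (days) | Power | Equivalent n per arm |
|---|---|---|---|---|
| 0 | 7.06 | 1.07 | 80.0% | 87 |
| 0.02 | 6.99 | 1.06 | 80.8% | 88.8 |
| 0.05 | 6.88 | 1.04 | 82.0% | 91.6 |
| 0.10 | 6.70 | 1.02 | 84.0% | 96.7 |
| 0.15 | 6.51 | 0.99 | 86.0% | 102.4 |
| 0.20 | 6.32 | 0.96 | 88.0% | 108.8 |

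The starting point is a comparison with no covariates. A model already containing age, gender and lung function would start from a different base, which the documents do not allow one to compute.

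**Chance imbalance.** Suppose one resection class has 30% prevalence (assumption). The SE of the between-arm difference in its share is √(2 × 0.3 × 0.7/87) = 0.069, about 7 percentage points. A gap of 10 points or more then has z = 0.10/0.0695 = 1.44, a two-sided probability of about 15%.

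**Degrees of freedom.** With 174 evaluable patients and single terms for treatment, age, gender and lung function plus an intercept, 174 − 5 = 169 remain. Planned extent takes 2, approach 1 and chemotherapy 1, leaving 165.

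**The case against.** A reader might infer that variation due to extent stays in the primary comparison because the linear model omits it. The documents do not support that. Length of stay is tested without covariates, so adding terms to the separate linear model would leave the t-test or Wilcoxon result exactly as it was. No power is gained on the primary test unless the adjusted model is named primary.

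A reader might also infer that an imbalance in extent would invalidate the result. It would not. Randomisation keeps the unadjusted test valid, and its standard error already allows for chance imbalance in unlisted variables. One major operative variable, approach, is also balanced by design.

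Two further objections stand. The size is conjecture: R² has no source, the SD is back-solved, and at R² = 0.02 the gain is under one percentage point. If stay is skewed, as 11.3.2 allows, these normal-theory figures do not carry over to Wilcoxon. And it is an inference that extent is settled before randomisation. Section 4.4 says only that surgery is scheduled, no passage says that planned extent is recorded or final, and it may differ from the operation performed, which would weaken it as a predictor.

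None of this defends the covariate list itself. Approach does not stand in for extent, since 3.2.1 allows either approach for any of the three resections. Nor do the documents give a reason for leaving two stratification factors out of the model.

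**Conclusion.** The point holds for the adjusted model only. It omits planned extent, a plausible baseline predictor that could be recorded at registration, and two factors that the protocol itself treats as important enough to stratify on. The omission of the stratification factors is the better documented half, because it rests on the protocol's own statement about imbalance.

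The loss is precision and robustness to chance imbalance in the adjusted estimate, and in the QOL models that reuse its covariates. It is not bias, and the unadjusted primary test stands as planned. The illustrative gain, from 80% to about 81-88%, rests on an assumed R² of 2-20%, a back-solved SD of about 7.06 days and 87 evaluable per arm. It shows a possible size and is not an estimate for this trial. This is an inexpensive improvement to the plan, not a failure of validity.

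**What to change.** Add a three-level field for planned extent (limited resection, lobectomy, pneumonectomy) to registration, completed before randomisation. In 11.3.2, add planned extent and the stratification factors to the adjusted length-of-stay model, and define the lung function term. Carry the same list into the QOL models in 11.4.1 and 11.4.2. Specify planned extent and not the procedure performed, and state in advance that pneumonectomy is pooled with lobectomy if sparse. State also whether the adjusted model is primary or supportive, since that decides whether any gain reaches the primary result.

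The cost is one extra registration field and two degrees of freedom for planned extent. Approach and neo-adjuvant chemotherapy are already needed for randomisation and take one degree of freedom each. The sample size and the unadjusted test do not change.
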